### 4.1.2 Secondary Study Endpoints

- Mean A1c and proportion of patients at goal at 3 months and 9 months.
- Mean FBG at 6 and 12 months compared to baseline value
- Mean BMI at 6 and 12 months compared to baseline
- Mean waist circumference at 6 and 12 months compared to baseline
  - Mean blood pressure at 6 and 12 months compared to baseline
  - Number and percentage of patients identified as potentially having the following complications:
  - Angina
    - Foot ulcers
    - Ophthalmologic complications
    - Hypertension
  - Percentage of patients successfully completing referrals for potential complications
- Number of patients referred for poor glycemic control or intolerance of diabetic medications and
  percentage of these patients who complete referral
- Prevalence of adverse effects of metformin and hypoglycemia symptoms throughout the study
- Patient medication adherence throughout the study and at 6 and 12 months compared to baseline
- CHW compliance with medication recommendations provided by the application (proportion of visits)

## 4.1.3 Primary Safety Endpoints

- Documented hypoglycemia (blood glucose <70 mg/dL)

- Hypoglycemia requiring emergency transport to the hospital and/or hospitalization
- Instances in which the application provided an incorrect recommendation
- Patient death

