### [name]

SLM hopes to continue this rural diabetes treatment program indefinitely, with the results of this study
informing a quality improvement process to ensure the provision of high quality care.

A potentially controversial aspect of this program is that CHWs will be making metformin and glibenclamide dose adjustments based on an algorithmic protocol, with physician oversight occurring in a retrospective fashion. However, this approach has been used safely and effectively for chronic disease management in LMIC. For example, a validation study of the WHO CVD-Risk Management Package in India found that frontline health workers following a treatment algorithm for hypertension made the same decision as a physician with regarding to prescribing a thiazide diuretic 88-97% of the time. Additionally, a diabetes treatment program in rural Guatemala working with indigenous patients, a population analogous to our target population, successfully utilized protocol-based care carried out by nurses to safely improve glycemic control and other treatment parameters.

We believe that the novel aspect of our intervention, the use of a smartphone application to guide treatment decisions, improves on these protocol-driven approaches in several ways. The use of a mobile computer-based algorithm as opposed to a paper algorithm allows for greater complexity and the incorporation of additional factors relevant to patient safety, such as the patient's current dose of medication, medication adherence, and medication side effects, in order to provide more specific recommendations. In this way, it decreases the cognitive burden placed on CHWs and the potential for human error. Rather than having to follow a complicated paper flowchart, CHWs will input information into the smartphone application, which will process the data and present the CHW with a concrete recommendation. Additionally, a computer-based system allows for easier review by the supervising physician and auditing and analysis of both program process measures and outcomes.

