## 2.7.2 Protection Against Risks

The risks of side effects from medications will be mitigated by several mechanisms:

- As decreased renal function increases the risk of adverse effects of metformin and glibenclamide, renal function testing will be required prior to administration of medications for patients with a history of kidney disease and recommended for patients with hypertension and/or duration of diabetes of 10 years or greater. Glibenclamide and metformin will not be used for patients with eGFR <30 mL/min.

- Patients will be asked about adverse effects of metformin monthly. Patients who are taking glibenclamide
  will also be asked about hypoglycemia symptoms and medication will be down-titrated if these symptoms
  are present
- Patients above the age of 65 will have a less stringent treatment goal of A1c ≤8%, in accordance with ADA guidelines.
- Medication will only be up-titrated at 1 month checks when blood glucose is significantly above glycemic goals: FBG >180 mg/dL or PPBG >300 for patients below age 65 and FBG >200 mg/dL or PPBG >300 for patients 65 or older or with multiple comorbidities
- For aspirin use, patients will be asked about history of aspirin allergy in potentially emergent situations (when patient presenting with chest pain that could represent ACS) and aspirin will not be administered to patients with history of allergy. In non-emergent situations, patients will be asked both about history of allergy and signs of GI bleeding (blood in stool or black and tarry stools) prior to dispensing aspirin.

The risks of POC finger stick testing will be minimized by CHW training emphasizing sterile technique and standard precautions.

The risks posed by application malfunction or incorrect use will be mitigated by an intensive alpha testing process (systematically testing each possible scenario prior to implementation with patients to ensure correct

Version #: 1.0

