### Physician Oversight

Within 1-2 days of the enrollment visit and every subsequent visit, patient data from the smartphone application will be uploaded to a secure online database viewable to the supervising physician, [name]. Within 1 week of each visit, [name] will review the visit summary for each patient and either approve the current treatment or recommend changes to the treatment, including changes to the patient's glycemic target as necessary. Also during that 1 week timeframe, any changes recommended by [name] will be communicated to the patient through the health promoter coordinators and/or the health promoter who saw the patient.

If CHWs have questions regarding patient care while conducting a patient visit, they will contact one of the CHW coordinators and or [name] via telephone for advice on how to proceed.

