## 8.2 Statistical Methods

The primary endpoints will be hemoglobin A1c at 6 months and 12 months post-enrollment. This will be analyzed and reported in two ways:

- Mean hemoglobin A1c in the study group compared to mean value at baseline
- Percentage of patients meeting treatment goal for hemoglobin A1c compared to this percentage at baseline. Treatment goal will be A1c ≤7 for most patients, A1c ≤8 for patients age 65 or older or who have 2 or more comorbidities, or other individualized goal for select patients as determined by the medical director ([name])

Secondary endpoints and analyses will include:

- Mean A1c and proportion of patients at goal at 3 months and 9 months.
- Mean FBG at 6 and 12 months compared to baseline value
- Mean BMI at 6 and 12 months compared to baseline
- Mean waist circumference at 6 and 12 months compared to baseline ٠
- Mean blood pressure at 6 and 12 months compared to baseline
- Number and percentage of patients identified as potentially having the following complications: Ischemic chest pain
  - 0
  - 0 Foot ulcers
  - Ophthalmologic complications 0
  - Hypertension 0
- Percentage of patients successfully completing referrals for potential complications
- Number and percentage of patients referred for poor glycemic control or intolerance of diabetic medications and percentage of these patients who complete referral
- Prevalence of adverse effects of metformin and hypoglycemia symptoms throughout the study
- Patient medication adherence throughout the study and at 6 and 12 months compared to baseline (proportion patient reporting each level of adherence)
- CHW compliance with medication recommendations provided by the application (proportion of visits)

Differences in continuous variables (e.g. mean A1c) will be analyzed using paired, 2-tailed t tests. Differences in categorical values (e.g. percentage of patients meeting treatment goal for A1c) will be analyzed using the McNemar test for binary matched-pairs data.

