The occurrence of documented hypoglycemia (including hypoglycemia requiring emergency transport to SLMH), hypoglycemia symptoms requiring the assistance of another person for treatment, signs of GI bleeding in patients taking aspirin, and other adverse effects reported by patients that are not consistent with GI side effects of metformin or mild hypoglycemia associated with glibenclamide (miscellaneous adverse effects) will be recorded through the smartphone application used for program execution and data entry. Treatment of hypoglycemia, including emergency transport if needed, will also be executed and recorded according to the hypoglycemia protocol (Appendix 4). Patients who require transport to SLMH will be assessed and treated by [name] and his staff, who will record treatments administered and patient outcomes, including need for hospitalization and any serious sequelae of the hypoglycemic event, including death. Patients taking aspirin who are experiencing possible GI bleeding will have their aspirin discontinued and will be referred to [name], who will record the results of any diagnostic evaluation and treatment required. Miscellaneous adverse effects of medications recorded by CHWs will be reviewed by [name] during his review of monthly patient visits (see section on "Physician supervision" in the Study Procedures section) and he will direct CHWs to take corrective action based on his clinical judgement.

Following each monthly visit, [name] will review treatment for all patients in the program. If the recommendations provided by the application and carried out by the CHWs goes against his clinical judgement, he will contact the CHW coordinators and direct them on corrective action. They will then visit the patient to follow up on their clinical status and carry out the actions recommended by [name]. When these corrective actions are necessary, [name] will communicate this to [name] and [name], who will record the reason that [name] disagreed with application recommendations and the corrective action that was recommended and carried out. Once per month, [name] will also review all treatment data to assess for compliance to program protocols, correctness of application treatment recommendations, and occurrence of adverse events. He will communicate his findings to [name] (PI), [name], [name], and the CHW coordinators in order to allow for corrective action and

Version #: 1.0

[name]

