### 10.4.4 Events of special interest

Events of special interest include documented hypoglycemia, probable hypoglycemia (symptoms reported by patient without hypoglycemia documented by blood glucose measurement) that required assistance from another person for treatment and incorrect recommendations given by the smartphone application.

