## 10.6 Safety Oversight

[name] will review all patient data each month to identify patient safety issues. Any issues will be promptly discussed with site investigator and medical director, [name], and with the PI, [name]. Special attention will be given to the following potential safety issues:

- Documented hypoglycemia. This includes those episodes requiring emergency patient transport (severe) and non-severe (those treated without complication in the field). While this is a known but side effect of glibenclamide, frequent occurrences in our patients may suggest the need for an alteration in our medication titration protocols
- Severe probable hypoglycemia (patient reports hypoglycemia symptoms that required the assistance of another person to treat due to altered mental status)
- Incorrect recommendations regarding medication dosing, management of complications, or recommendations for referral provided by the application
- AEs and UPs as described above, which would also be reported to the IRB.

Interim cumulative safety analysis will occur at 3 months, 6 months, and 9 months and final safety analysis at 12 months.

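### The safety endpoint counting incorrect application recommendations has no stated reference standard or denominator, and the plan does not say whether logged physician disagreements count

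*Combined protocol and SAP*

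**What the plan says.** Section 3 makes the safety of medication titration by community health workers (CHWs) using the application a secondary objective. Section 4.1.3 lists four primary safety endpoints, one of which is "Instances in which the application provided an incorrect recommendation". Section 10.1 lists it again in the same words. Section 10.4.4 makes "incorrect recommendations given by the smartphone application" events of special interest. Section 10.6 asks for special attention to "Incorrect recommendations regarding medication dosing, management of complications" and referral. None of these sections defines incorrect. Section 8.2 gives no analysis, unit or denominator for the endpoint.

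Three other places bear on what the word might mean:

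- Section 2.7.2 describes alpha testing before launch: "systematically testing each possible scenario prior to implementation with patients to ensure correct" output in every case.
- Under Physician Oversight in section 7.4.1, the supervising physician reviews each visit within a week and must "either approve the current treatment or recommend changes to the treatment".
- Section 10.3 says that, where corrective action is needed, the study team records why the physician "disagreed with application recommendations and the corrective action that was recommended and carried out". The same section describes a separate monthly review that includes the correctness of application recommendations. It states no criterion for that review.

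**The concern.** An endpoint that counts errors needs a standard to judge against. Two are available here. One is the programmed algorithm, in which case an error is a software departure. The other is the physician's judgement, in which case an error is a recommendation he would not have made. They answer different questions and can give very different counts. With neither adopted, the choice could be made after the data are seen.

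If the algorithm is the standard, a row that is faithfully programmed but clinically unacceptable is not an error. The neighbouring process endpoint does not fill the gap, because CHW compliance compares the CHW's action with the application's output. No endpoint would then ask whether the recommendation itself was acceptable, although that bears directly on the safety objective. The physician's disagreements, which could answer it, are collected but assigned to no endpoint or analysis.

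Section 2.1 supports algorithm-guided care by citing a hypertension study in which frontline health workers "made the same decision as a physician with regarding to prescribing a thiazide diuretic 88-97% of the time". The plan does not propose to estimate the corresponding agreement in its own data.

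**Working it through.** The plan gives no rate, threshold or power for this endpoint, so there is no stated figure to reproduce. The check has two parts.

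**1. Would a conformity standard miss anything?** Two places in the appendices conflict with the body of the protocol.

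| Appendix text | Protocol text |
|---|---|
| Appendix 8, block for A1c 9 to 14, row 11d: a patient on metformin 1500-2000 mg plus glibenclamide 15-20 mg stays on the current glibenclamide dose | Section 2.6: the program's maximum glibenclamide dose is 10 mg per day |
| Appendix 6, Chest Pain: a yes to the aspirin allergy question leads to aspirin being given, a no to its being withheld | Section 2.7.2: aspirin is not given to patients with a history of allergy |

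No view is taken here on which text is right; each pair must be reconciled. For the endpoint, software that reproduces either appendix entry exactly conforms to the algorithm. It would score zero incorrect recommendations, and a CHW who followed it would score as compliant.

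**2. How far apart could the two counts be?** This is an illustration under assumptions.

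- Patients: 100, the minimum enrollment hoped for in section 8.1.
- Visits per patient to month 6: 1 enrollment + 6 monthly = 7.
- Physician disagreement: 100% − 97% = 3% to 100% − 88% = 12%. This comes from the study cited in section 2.1, which concerned thiazide prescribing, so its use here is an assumption.

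Expected count = patients × visits × disagreement rate.

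- Visits: 100 × 7 = 700.
- At 3%: 700 × 0.03 = 21. Exact (Clopper-Pearson) 95% CI 1.9% to 4.5%.
- At 12%: 700 × 0.12 = 84. Exact 95% CI 9.7% to 14.6%.
- At 1%, as a lower case: 700 × 0.01 = 7.
- Followed to month 12 (13 visits): 100 × 13 = 1,300 visits, giving 39 at 3% and 156 at 12%.
- Under conformity with the algorithm: about 0 in every case, if the software runs as programmed.

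These intervals treat visits as independent. Visits cluster within patients, so they are too narrow. The extreme case is complete dependence, where each patient contributes one effective observation (n = 100). Then 3 of 100 gives 0.6% to 8.5%, and 12 of 100 gives 6.4% to 20.0%. The truth lies between, which is why a clustered interval is needed.

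**The case against.** A reader might infer three stronger things that the documents do not support.

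*That the plan defines correct as matching the algorithm, so the count must stay near zero.* No section adopts that definition. The alpha-testing sentence in section 2.7.2 concerns mitigation of malfunction and misuse, and it goes on to name physician oversight as a further safeguard. Section 10.6 describes incorrect recommendations in clinical terms, and section 11.1.1 monitors their accuracy. The disagreement log may well have been meant to feed the count. The near-zero figure holds only under the conformity reading.

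*That the physician's verdict is already on record for every visit.* Section 7.4.1 requires review of every visit, but section 10.3 requires recording only of disagreements that need corrective action. Nothing says that approvals are logged, so the denominator may not exist.

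*That the trial cannot detect unsafe titration.* Documented hypoglycemia, hypoglycemia needing transport or hospitalization, and death are also primary safety endpoints. Section 10.5 sets a review trigger of more than 3 severe hypoglycemia episodes. These would pick up some of the harm from an unsuitable row. They would not show undertreatment or a missed referral.

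It is also fair to say that a physician-based measure is imperfect. The medical director approved the algorithm and sees its output before judging, so he is not an independent reference. Sections 4.1.1 and 7.4.1 let him individualize glycemic targets, so some changes are not errors. Both points stand. They argue for classifying the changes and stating the limitation, not for leaving the endpoint undefined.

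**Conclusion.** The concern holds in this form: a primary safety endpoint has no stated reference standard and no denominator, and the plan does not say whether the physician disagreements it collects count towards it. That much rests on the text alone.

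The size is illustrative. With 700 visits and an assumed 3-12% disagreement, the undefined word separates a count of about 0 from one of 21 to 84. The documents give no disagreement rate for this setting, and the borrowed range should not be read as a forecast. The conditional part, that a conformity standard would pass clinically unacceptable rows, is made concrete by the two appendix entries that contradict the protocol's text.

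The sponsor should make this change. It goes beyond adding a definition, because it puts data that are largely collected already to work on a stated objective.

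**What to change.** In sections 4.1.3, 8.2 and 10.1, replace the single count with two measures, reported separately:

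- **(a) Physician change.** The proportion of physician-reviewed visits at which the supervising physician changed the application's recommendation. Split it by type: dose judged too high, dose judged too low, referral or complication handling, and individualized target. Give a 95% CI from a method that allows for clustering by patient.
- **(b) Software departure.** The number of application outputs that differ from the approved algorithm, over outputs checked.

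State that disagreements logged under section 10.3 feed (a). Add a field recording completion of each review (approve or change), made against the application's output, so that the denominator exists. Separately, reconcile Appendix 8 row 11d (A1c 9 to 14) with section 2.6, and the Appendix 6 aspirin step with section 2.7.2, so that the approved algorithm used in (b) is unambiguous.

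The cost is protocol wording, one small recording field and one extra table; no treatment changes. There are two downsides. The reported figure will probably look less favourable than a malfunction count. The reference in (a) is also not independent, since the physician approved the algorithm and sees its output, and the report should say so as a limitation.

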# 5 Study Subjects – Enrollment and Withdrawal

## 5.1 Subject Population

Subjects will include adults 18 years of age and older and will be recruited from the 19 rural villages surrounding San Lucas Tolimán, Guatemala. Treatment of children with diabetes entails greater complexity and is beyond the scope of this program. Though there are no enrollment restrictions based on race or ethnicity, the majority of the people living in these villages are from the Kaqchikel ethnic group, an indigenous Mayan people of the midwestern highlands of Guatemala.

Version #: 1.0

[name]

# 5.2 Inclusion Criteria

Inclusion Criteria		
1	Willing to provide written informed consent	
2	Willing to comply with all study procedures and be available for the duration of the study	
3	Male or female, at least 18 years of age	
4	Prior diagnosis of type 2 diabetes	
5	Resident of one of the rural communities served by the CHW network of San Lucas Tolimán	
	*	

# 5.3 Exclusion Criteria

Exclusion Criteria		
1.	Type 1 diabetes	
2.	Women who are pregnant	
3.	Current use of insulin	
4.	Renal insufficiency (eGRF <30 mL/min/1.73 m 	
5.	Unable to provide informed consent	

# 5.4 Subject Screening for Recruitment

## 5.4.1 Subject Identification

Potential subjects will be identified by CHWs from their prior knowledge of individuals with diabetes in their communities. We also anticipate that study participation will be bolstered by word of mouth communication between patients in the communities. Patients may also be identified during mobile medical clinics run by visiting medical volunteers.

## 5.4.2 Recruitment and Retention Strategies

Potential participants will be contacted in person by CHWs. At that time, the health promoter will ask if they would like to participate in the study. We anticipate that more than women than men will enroll in the study based on prior experience of the CHWs in other health promotion programs. Men's availability is often less than women's because of their occupations (agricultural work with long and inflexible hours, long commutes or residential work in population centers). The communities we are working in are ethnically homogenous, so recruitment of minorities is not relevant. We anticipate recruiting around 150 patients.

## 5.5 Vulnerable Populations

**TABLE 1:** Vulnerable populations included and excluded from this study:

Include	Exclude	Vulnerable Population Type
	Х	Adults unable to consent
	Х	Individuals who are not yet adults (e.g. infants, children, teenagers)
	Х	Wards of the State (e.g. foster children)
	Х	Pregnant women
	Х	Prisoners

Version #: 1.0

[name]

